### 5.2 Ethical implementation of the clinical trial

This clinical trial is to be carried out in compliance with the Sponsor's (or its representative's) SOP that was created in accordance with the following guidelines, etc.

- Ethical principles based on the WMA Declaration of Helsinki (Ethical Principles for Medical Research Involving Human Subjects)
- · ICH GCP (CPMP/ICH/135/95)
- All clinical trials carried out in European countries shall adhere to European Good Clinical Practice Directive 2005/28/EC and European Clinical Trial Directive 2001/20/EC. All suspected unexpected serious adverse reactions (SUSARs) are to be reported to competent authorities of involved European countries in accordance with the regulations

### 5.3 Information provided to subjects and informed consent

The Principal Investigator, in accordance with the ICH GCP (Section 4) and regulations of each region, shall create an informed consent form with the help of the Sponsor and obtain approval of the IRB/IEC.

The Principal Investigator or the Sub-investigator is required to explain to each subject (or representative) the clinical trial content, purpose, procedures, scheduled participation period, anticipated clinical benefits, risks and inconveniences, whether there are other treatment methods available to the subject, and the fact that the subject's confidentiality will be protected. The Principal Investigator or the Sub-investigator shall also explain that the subject's participation in the clinical trial is voluntary, that the subject may refuse to participate or withdraw from the trial at any time, and that the refusal or withdrawal will not adversely affect the subject's subsequent medical treatment or relationship with the doctor. A document written in a non-specialised language shall be used in the above informed consent explanation.

Before participation in the trial, the subject is to sign his/her name and date the informed consent form that has been approved by the IRB/IEC/IEC. The informed consent form must also be signed and dated by the Principal Investigator or authorized Sub-investigator who conducted the informed consent discussion. The subject needs to understand the explanation before writing his/her signature and date on the form. The subject is to receive a copy of the signed informed consent form and subject information sheet. If the subject is unable to read the informed consent form, an impartial witness needs to be present throughout the entire informed consent explanation process. The witness is to read out and explain to the subject the informed consent form and other information for the subject contained in documents. Afterwards, the subject is to give a verbal consent to participate in the study. Then, the witness is to write his/her signature and date on the consent form after the subject, if he/she is able to, has written his/her signature and date on the form. Before carrying out any assessments and evaluations related to this clinical trial, it is necessary to confirm whether the subject has signed the informed consent form. The subject may not be enrolled in the clinical trial before signing his/her informed consent.

The original of all signed informed consent form are to be stored at the Clinical Trial Centre, and this is to be verified by the Sponsor.

If any information that might affect the subject's willingness to continue participation in this clinical trial becomes available, the information is to be promptly provided to the subject, and the fact of its

provision is to be recorded in writing.

In cases where the consent of a legally acceptable representative is required, if the subject understands the fact of his/her participation in the clinical trial, the Principal Investigator or Sub-investigator shall use the informed consent form to explain about the clinical trial to the subject in the same way he did to the legally acceptable representative, and obtain the subject's signature. Subjects who are unable to sign the consent form are to verbally confirm their willingness to participate, which is to be recorded in the consent form.

### 6. Principal Investigators and the Clinical Research Associates

This clinical trial will be conducted at 18 Clinical Trial sites (anticipated) in Japan, Europe and Russia by Principal Investigators selected by the Sponsor (Attachment 1).

The name and contact information (telephone number and FAX number) of the Sponsor and Contract Research Organization (CRO) are listed in Attachment 2.

#### 7. Introduction

Crohn's disease is one of inflammatory bowel diseases (IBD) that causes longitudinal ulcers in the small and large intestine, which leads to abdominal pain, diarrhoea, fever, melena and weight loss. The disease commonly occurs in people in their 10s and 20s. The patients experience repeated recurrences that cause a progressive destruction of the gastrointestinal tract tissue, which ultimately necessitates a resection. The cause of Crohn's disease is not known, but it is thought to be a multifactorial disease caused by an intricate combination of genetic factors, environmental factors such as diet, and increased inflammatory cytokines such as tumour necrosis factor (TNF $\alpha$ ) associated with immunological abnormality. The number of Crohn's disease patients in Japan has been growing each year, with approximately 41,000 patients as of present (2014, number of medical care certificate holders). This disease is especially prevalent in Europe and America, where the incidence rate is high.

At present, there is no cure for Crohn's disease, and the goal of the treatment is to prevent recurrence, control disease activity and maintain clinical remission. Biologics such as anti-TNF  $\alpha$  antibody products have greatly changed the therapeutic system, as they were found to be effective in Crohn's disease patients who did not derive sufficient benefits from existing therapeutic drugs, including steroids or immunomodulators. However, there are also patients who do not respond to such biologics, patients for whom the therapeutic efficacy decreases  $^3$ , and patients for whom administration cannot be continued due to allergic reactions. As such, it cannot be said that biologics sufficiently meet medical needs. Consequently, there is a strong demand for development of drugs with new mechanisms of action that are highly effective and safe.

E6011 is the world's first humanised anti-fractalkine (FKN) monoclonal antibody created by Eisai's KAN Research Institute, Inc. FKN has a dual effect of modulating leukocyte migration and acting as an adhesion molecule, and plays an important role in leukocyte infiltration in the inflamed tissue. From the fact that anti-FKN antibody suppressed damage to large intestine in mouse models of T cell transfer colitis and oxazolone-induced colitis, it has been suggested that FKN plays a role in intestinal inflammation . In

Date: 18-Apr-2022 version 11.0 Confidential Page 23 of 80

addition, FKN expression and FKN receptor (CX3CR1) positive cells are increased in Crohn's disease patients' peripheral blood and inflamed gastrointestinal tract tissue, which points out to a relationship between the pathology of Crohn's disease and FKN. Based on the above, it is expected that E6011, by inhibiting FKN function, will suppress migration and infiltration of lymphocytes and monocytes into inflammatory sites, thus reducing inflammatory lesions in the gastrointestinal tract of Crohn's disease patients.

At present, a phase 1 study of single intravenous (IV) E6011 administration in Japanese healthy adult subjects (E6011-J081-001, hereinafter "Study 001") and a phase 1 study of single subcutaneous administration (SC) in healthy Japanese adult subjects (E6011-J081-002, hereinafter "Study 002") have been completed. No adverse events that raise concerns in terms of safety and tolerability were observed with the dosages used in Study 001 (IV: 0.0006 to 10 mg/kg) and Study 002 (SC: 50 to 400 mg).

In a phase 1/2 study of repeated intravenous E6011 administration in Japanese subjects with Crohn's disease (E6011-J081-101, hereinafter "Study 101"), safety and tolerability upon administering 2 mg/kg, 5 mg/kg, 10 mg/kg and 15 mg/kg of E6011 were evaluated as primary objectives. Analysis of the 12-week administration has been completed, and there were no safety or tolerability problems concerning Crohn's disease with the 2 to 15 mg/kg repeated administration. In addition, exploratory evaluation of efficacy showed a trend towards improvement in the clinical symptoms of Crohn's disease.

Based on the above results and in view of the present demand for a Crohn's disease drug with a new mechanism of action in terms of efficacy and safety, a double-blind, placebo-controlled, parallel-group clinical trial has been designed to evaluate the efficacy and safety of E6011, which is a new drug expected to benefit Crohn's disease patients. Due to the number of Crohn's disease patients being smaller in Japan compared to Europe and America, making it difficult to enrol subjects in Japan alone, and due to the fact that the next phase of the clinical trial is going to be focused on non-Japanese patients, this clinical trial has been designed as a multinational clinical trial with added participation of European countries.

#### 8. Clinical trial objective

To perform the following evaluation after administering E6011 to patients with moderate to severe active Crohn's disease.

### 8.1 Primary objective

To examine the efficacy and safety of E6011 at 12 weeks after administration by means of double-blind placebo-controlled trial.

#### 8.2 Secondary objective

- To examine the efficacy and safety of a long-term administration of E6011.
- To evaluate the pharmacokinetics and immunogenicity of E6011.

### 8.3 Exploratory objective

#### 9. Clinical trial plan

### 9.1 General clinical trial design and plan

This is a multinational, multicentre, randomised, double-blind, placebo-controlled, parallel-group, early phase 2 clinical trial. This clinical trial consists of a screening period, remission-induction period (double blind), rescue period (open-label), extension period (open-label), post-observation period and follow-up period. Administration of the IMP is to start after confirming eligibility at baseline (at week 0 before the start of the IMP administration) upon having carried out the screening test within 42 days prior to the start of the IMP administration after obtaining consent.

Patients with moderate to severe active Crohn's disease are to be randomly allocated to an E6011 10mg/kg group and a placebo group (1:1) using stratified allocation in which race (Japanese/non-Japanese) and history of previous use of biologics (yes/no) are used as allocation factors. The administration volume (about 100 mL) is to be prepared based on the weight of the subject by diluting E6011 with a physiological saline solution, and infused intravenously over approximately 30 minutes. The physiological saline solution used to dilute E6011 is to be used as a placebo. The remission-induction period is to last 12 weeks, with E6011 or placebo administered in a double-blind method on Week 0, Week 1, Week 2, and once every two subsequent weeks up to Week 10, and the efficacy of E6011 is to be evaluated in Week 12. Subjects with a reduction in the CDAI (Crohn's Disease Activity Index) of 70 or more (responders) compared to baseline at evaluation on Week 12 are to move on to the open-label extension period. The extension period is to last 40 weeks, with 10 mg/kg of E6011 administered every four weeks from Week 12 to Week 48 and E6011 efficacy is to be evaluated at Week 52.

Subjects with less than 70 reduction in the CDAI (non-responders) at evaluation in Week 12 are to move on to the rescue period. The rescue period is to last 12 weeks, with additional administrations of 10 mg/kg of E6011 in Week 12, Week 13, Week 14 and every two subsequent weeks up to Week 22. Subjects with a reduction in the CDAI of 70 or more compared to baseline/Week 12 at evaluation in Week 24 of the rescue period are to move on to the open-label extension period. The extension period is to last 40 weeks, with 10 mg/kg of E6011 administered every four weeks from Week 24 to Week 60 and E6011 efficacy is to be evaluated at Week 64. Patients with less than 70 reduction in the CDAI compared to baseline and Week 12 at evaluation in Week 24 are to be discontinued.

[figure not shown]
The Principal Investigator or Sub-investigator is to confirm that the subjects' data as of Week 12 of the remission-induction period (double-blind) has been completely entered into the eCRF by the time the first evaluation in the rescue period or extension period takes place. Blinding in the double-blind period is to be maintained until a database in the double-blind study period is locked.

The post-observation period consists of an assessment in person 28 days after the completion or discontinuation of the extension period of the clinical trial, and an assessment in person or over the phone 70 days after the last administration of the IMP. The follow-up period entails contacting the patients over the phone, etc. every 6 months until 2 years have passed from the last administration of the IMP to inquire whether they have experienced progressive multifocal leukoencephalopathy (PML).

Date: 18-Apr-2022 version 11.0 Confidential Page 25 of 80

Figure 1 shows the design of the clinical trial.

Figure 1 Clinical trial design

Responders at CDAI evaluation on Week 12 of the remission-induction period are to move on to the extension period, in which E6011 is administered every four weeks. Non-responders are to move on to the rescue period, and if the CDAI has improved by Week 24, they are to move on to the extension period, in which E6011 administered every four weeks. Subjects whose CDAI has not improved by Week 24 are to be discontinued.

### 9.1.1 Screening period

After the clinical trial has been sufficiently explained to each subject, a written consent is to be obtained from each subject before carrying out any assessments and evaluations related to this clinical trial. Section 5.3 describes procedures related to obtaining consent.

Patients who signed consent are to undergo screening period tests in between 42 days and one day before the start of the IMP administration. The Principal Investigator or Sub-investigator is to confirm whether each subject meets all inclusion criteria and does not fall under any of the exclusion criteria.

Screening results are to be recorded in the case report form. If a subject is deemed not eligible to participate in this clinical trial, the reason is to be recorded in the case report form.

Because subjects deemed to require prophylactic administrations of isoniazid as a result of tuberculosis check-up in the screening period will start receiving the IMP after more than 21 days of prophylactic administration, the screening period may be extended until 21 days have passed from starting isoniazid (Prophylactic treatment should be given in accordance with the local guidelines).

#### 9.1.2 Remission-induction period

Subjects who were deemed eligible to participate in the screening period and at baseline are to be allocated to the E6011 10 mg/kg group and placebo group at the ratio of 1:1 using stratified allocation in which race and history of previous use of biologics are used as allocation factors. E6011 or placebo is to be administered to allocated subjects in a double-blind method on Week 0, Week 1, Week 2, and every two subsequent weeks until Week 10.

Date: 18-Apr-2022 version 11.0 Confidential Page 26 of 80

### 9.1.3 Rescue period

Subjects with a reduction in the CDAI of less than 70 compared to baseline after finishing evaluation in Week 12 of the remission-induction period are to move on to the rescue period. The rescue period is to last 12 weeks, with 10 mg/kg of E6011 administered in an unblinded manner on Week 12, Week 13, Week 14 and every two subsequent weeks until Week 22.

The Principal Investigator or Sub-investigator is to confirm before the first evaluation in the rescue period is carried out that non-responders' data up to Week 12 of the remission-induction period (double-blind period) has been entered in the case report form. Blinding of each subject's treatment group is to be maintained until the database of the remission-induction period is locked.

Subjects with a reduction in the CDAI of 70 or more compared to baseline or Week 12 at evaluation in Week 24 are to move on to the extension period. Subjects with less than 70 reduction in the CDAI compared to baseline and Week 12 are to be discontinued.

#### 9.1.4 Extension period

Subjects who finished evaluation at Week 12 of the remission-induction period and had a CDAI response of 70 or more, and subjects who moved on to the rescue period and finished evaluation at Week 24 with a CDAI response of 70 or more are to move on to their respective extension period. The extension period is to last 40 weeks, with 10 mg/kg E6011 administered in an unblinded manner every four weeks up to Week 48 or Week 60.

The Principal Investigator or Sub-investigator is to confirm before the first evaluation in the extension period is carried out that responders' data up to Week 12 of the remission-induction period (double-blind period) has been entered in the case report form. Blinding of each subject's treatment group is to be maintained until the database of the remission-induction period is locked.

#### 9.1.5 Post-observation period

After the extension period of the clinical trial has been finished or discontinued, examinations are to be carried out 28 days after the completion or discontinuation of the extension period (in the hospital) and 70 days after the last administration of the IMP (in the hospital or over a telephone call).

#### 9.1.6 Follow-up period

PML onset is to be investigated over the phone, etc. every 6 months in the two-year follow-up period after the last IMP administration.

#### 9.2 Discussion of the clinical trial design, including control group selection

This is a multinational, multicenter, randomised, double-blind, placebo-controlled, parallel-group, clinical trial with the primary objective of evaluating the efficacy and safety of E6011 in patients with moderate to severe active Crohn's disease.

In Japan's Crohn's disease treatment guidelines, oral adrenocorticosteroids (including budesonide), nutritional therapy and immunomodulators are used as remission-induction therapy in moderate to severe

Date: 18-Apr-2022 version 11.0 Confidential Page 27 of 80

active Crohn's disease. Antibacterial drugs and apheresis are sometimes used as concomitant therapies. If oral adrenocorticosteroids and nutritional therapy are not effective, the use of anti-TNF $\alpha$  antibody biologics is recommended on the other hand, ECCO guidelines suggest using vedolizumab, an anti- $\alpha$ 4 $\beta$ 7 integrin antibody, as well as anti-TNF $\alpha$  antibody as biologics for the treatment of active Crohn's disease Recently, ustekinumab, an anti-IL-12/23 antibody, is beginning to be used as a drug indicated for Crohn's disease. As such, this clinical trial will be conducted to evaluate the efficacy of E6011 administration in patients with moderate to severe active Crohn's disease who were not deriving satisfactory benefits from the use of existing drugs (adrenocorticosteroids, immunomodulative drugs, or biologics).

In this clinical trial, randomisation is to take place to eliminate bias in allocating subjects to treatment groups, to maintain balance in subject characteristics between the groups, and in order to improve validity of statistical comparison of the groups. Further, stratified allocation is to be performed in which race and history of biologic use, which might influence the efficacy evaluation, are used as allocation factors. In order to minimise the possibility of bias in data collection and endpoint evaluation, treatment groups are to be blinded.

EMA's Guidelines on the development of new medicinal products for Crohn's disease state that "it is desirable that clinical symptoms in the active disease period improve within 12 weeks".  As the results of Study 101 suggested that E6011 may be effective when administered for 12 weeks, evaluation period in the remission-induction period of this clinical trial was set to 12 weeks, with the primary endpoint as the ratio of subjects who had CDAI reductions of at least 100 points from basline at Week 12 (CR100 response rate).

Due to the fact that the subjects of this clinical trial were patients that did not derive sufficient benefits from treatment with existing drugs, an extension period of 40 weeks maximum was designed for subjects whose CDAI improve after the end of the 12-week remission-induction period (responders). A rescue period was also designed for subjects who do not show improvement in CDAI in the remission-induction period (non-responders) so that they would be able to receive E6011 in the same form and dosage as in the remission-induction period. The design is such that those subjects whose CDAI improve in the rescue period will move on to the extension period. It was decided that a design allowing both responders and non-responders to receive E6011 after the 12-week remission-induction period would be beneficial for the patients.

The post-observation period was set as 70 days after the last administration of the IMP, because of approximately five times the length of the longest observed half-life period of E6011. A follow-up period was designed to entail checking for the onset of PML, which is an anticipated risk of E6011, for two years after the last administration of the IMP.

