# 9.7.1.6.1 Analysis of primary efficacy endpoint

For Week 12 CR100 response rate, the Bayesian posterior distribution of the difference in the CR100 rate at Week 12 between the E6011 group and the placebo group is to be calculated. If there was a 50% or

Date: 18-Apr-2022 version 11.0 Confidential Page 67 of 80

more probability of the difference between both groups being 25% or more, the efficacy of E6011 is confirmed. Noninformative prior distribution is to be used for both the E6011 group and the placebo group.

Subjects with missing primary endpoint data due to premature discontinuation before 12 weeks after administration or other reasons are treated as non-responders - non-responder imputation (NRI).

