6.8.1 Primary Efficacy analysis

Primary analysis aims to determine if the treatment effect in CR100 response rate at Week 12 is expected to be higher for patients treated with E6011 than for patients treated with placebo.

The Bayesian posterior distribution of the difference in the CR100 rate at Week 12 between E6011 (p1) and placebo (p2) is obtained as p1-p2 posterior distributions. Non-informative prior (Jeffreys) Beta (1/2, 1/2) distributions described by (Oleksandr Sverdlov, Yevgen Ryeznik, & Sheng Wu, January 1, 2015) will be used to calculate p1 and p2 posterior distributions.

A MCMC algorithm will be performed using the following parameters:

- Number of chains = 3
- Initial values for the algorithm in every chain= 3 starting values simulated by a Beta (0.5, 0.5)
- Number of Burn-in = 100000

- Number of Iterations = 200000

Diagnostic for the MCMC convergence will be checked through the Geweke Diagnostics test, Raftery-Lewis Diagnostics, Gelman-Rubin convergence and the autocorrelation efficiency. In case of any issue due to an autocorrelation or non-convergence of the algorithm, the size of the burn-in, the number of iterations and a possible thinning will be evaluated.

Efficacy of E6011 will be confirmed if there was a 50% or more probability of the difference between both groups being 25% according to the posterior distribution.

Probability of the difference between groups being greater than zero will be also calculated.

Subjects with missing primary endpoint data due to premature discontinuation before 12 weeks after administration, or other reasons are treated as non-responders (NRI) in the modeling of the endpoint.

Primary analysis will be performed in the FAS population, and in the PPS population as a supportive analysis.

Two sensitivity analysis will be performed a Last Observation Carried Forward (LOCF) and an Observed Case (OC) imputation for CDAI at week 12 will be used instead of NRI.

Another supportive analysis will be performed following the same logistic regression model (randomization strata and treatment group as fixed factor) used in the secondary analysis.

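### No planned analysis adjusts CR100 for prior biologic use, and none gives a stratum-adjusted result on the 25-percentage-point scale, although allocation is stratified on race and biologic history

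*Protocol*

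**What the plan says.** Protocol 9.1 allocates patients 1:1 "using stratified allocation in which race (Japanese/non-Japanese) and history of previous use of biologics (yes/no) are used as allocation factors", which makes four strata. Section 9.2 gives the reason: "race and history of biologic use, which might influence the efficacy evaluation, are used as allocation factors".

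The deciding analysis does not use these factors. In SAP 6.8.1 the posterior of the CR100 difference "between E6011 (p1) and placebo (p2) is obtained as p1-p2 posterior distributions", with "Non-informative prior (Jeffreys) Beta (1/2, 1/2) distributions described by" a cited methods paper, one prior per arm. Protocol 9.7.1.6.1 sets the rule: if there is a 50% or "more probability of the difference between both groups being 25% or more, the efficacy of E6011 is confirmed". Protocol 9.7.2 reduces the sample from 40 to 25 and keeps the analysis plan as it was.

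SAP 6.8.1 adds: "Another supportive analysis will be performed following the same logistic regression model", with randomisation strata and treatment as factors. SAP 6.8.2 defines that model. It estimates an odds ratio, and its strata are written as Japanese/non-Japanese and male/female. SAP 6.11 reports no modification from the protocol.

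**The concern.** Two factors were judged important enough to randomise within, and the analysis then leaves them out. Whatever imbalance remains in race or biologic history enters the raw difference uncorrected. The cut is a posterior probability of 0.50, so the verdict turns on where the posterior is centred, and a shift of a few points can decide a result near the cut.

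The supportive model does not fill the gap. An odds ratio cannot be compared with a 25-point threshold. As the strata are written, race is adjusted for but biologic history is not. A reader of the study report would have no prespecified way to see whether a result close to the cut survives adjustment for the factors used in allocation.

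**Working it through.** **1. The plan's own figure.** The posterior in arm k is Beta(x_k + ½, n_k − x_k + ½), and success is P(p1 − p2 ≥ 0.25) ≥ 0.50. With 20 per arm, success needs at least 6 more responders on E6011. At a true difference of 40 points, exact enumeration gives a success probability of 0.807 to 0.874 for placebo rates of 5 to 60%, with the minimum at 30%. The stated figure of above 80% is reproduced.

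**2. How fine the cut is at 25 patients.** The arm split is not given; 12 v 13 is assumed. One patient is worth 1/12 or 1/13, about 8 points.
- 6/12 v 3/13 (difference 26.9 points): P = 0.509, confirmed.
- 5/12 v 2/13 (difference 26.3 points): P = 0.491, not confirmed.

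**3. How much imbalance is left.** From Protocol 9.3: 22/40 Japanese and 8/40 biologic-naive, both rough estimates. Assumed, because the documents do not give them: permuted blocks, independent factors, placebo rate 30%, and CR100 gaps of 20 points (naive v experienced) and 10 points (race).

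Shift = 20 × (difference between arms in naive share) + 10 × (difference between arms in Japanese share), in points.

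| Allocation, N = 25 | 95% range of shift | Shift above 5 points |
|---|---|---|
| No stratification | about ±7.7 | 18–19% |
| Stratified, blocks of 2 | about ±2.7 | 0% |
| Stratified, blocks of 4 | about ±3.8 | about 1% |
| Stratified, blocks of 6 | about ±4.7 | about 3% |
| Stratified, blocks of 4, gaps 30 and 20 | about ±6 | 11% |

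The mean shift is zero. At a true difference of 25 points, the planned rule confirms in 0.49 to 0.52 of trials under stratified blocks, against 0.50 when neither factor is prognostic. A second set of assumptions (blocks of 4, CR100 odds 3.3 to 6 times higher in naive patients) puts the 95th percentile of the shift at 4 to 7 points.

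**4. How often adjustment changes the verdict.** The same Bayesian logistic model (prior SD 2.5, blocks of 4, standardised to a risk difference) was run with and without the two factors.

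| True difference | Verdict changes | P(success), without → with factors |
|---|---|---|
| 0 | 2% | 0.045 → 0.038 |
| 25 points | 6% | 0.407 → 0.378 |
| 40 points | 4% | 0.709 → 0.696 |

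The planned Beta posterior gives 0.069, 0.506 and 0.802 in these trials. Most of the distance from the logistic results comes from the model and its prior, because the logistic model without factors is also lower. With a wide treatment prior (SD 10) and the second set of assumptions, crude and adjusted verdicts differ in about 5% of trials near 25 points, 3% at 38 points and 2% under no effect. The chance of confirming is then 50% against 52% near the threshold and 79% against 79% at 38 points.

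**5. Illustration (invented data).** E6011 7/13 (naive 4/4, experienced 3/9); placebo 3/12 (naive 1/2, experienced 2/10).
- Crude difference: 0.538 − 0.250 = 28.8 points. The SAP rule gives P = 0.549, confirmed.
- Standardised to 6 naive and 19 experienced: (0.24 × 1 + 0.76 × 0.333) − (0.24 × 0.5 + 0.76 × 0.2) = 0.493 − 0.272 = 22.1 points.
- Logistic model adjusted for biologic history, treatment prior SD 10: P = 0.44 with factor prior SD 2.5 and 0.41 with SD 5, not confirmed. Without the factor the same model gives 0.59, so the reversal comes from the adjustment.

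These data imply a treatment-adjusted odds ratio of about 13 for naive v experienced, above the assumed 3.3 to 6. Moving one E6011 responder from naive to experienced (3/4 and 4/9) brings it to 3.8. The standardised difference is then (0.24 × 0.75 + 0.76 × 0.444) − 0.272 = 24.6 points, and the adjusted probability is 0.505 (factor SD 2.5) or 0.493 (SD 5). Inside the assumed range, adjustment leaves the case on the cut.

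**The case against.** The strongest reply is that an unadjusted posterior is a legitimate prespecified choice. It meets the stated operating characteristic at 20 per arm, Protocol 9.7.2 retains it at 25 patients, and SAP 6.1 calls the analysis exploratory. Stratified allocation is itself the protection against imbalance. This stands, and it is a reason not to replace the decision rule.

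The adjusted posterior also depends on its priors at this sample size. In the illustration, with treatment prior SD 10, a factor prior SD of 1 gives 0.51 (confirmed) against 0.44 at SD 2.5. Cutting the treatment prior SD to 2.5, with factor SD 2.5, gives 0.36. The protocol asks for noninformative priors. This stands too, and it limits the analysis to a supporting role.

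SAP 6.1 also plans efficacy tables by previous biologics and by Japanese race, so response by arm within each factor would be visible. This stands in part. The tables are descriptive and correct nothing, and results are withheld for subgroups of fewer than 5 patients. At 8/40, about 5 of 25 patients would be biologic-naive, so that table may not appear.

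A reader might go further and infer that stratum imbalance feeds straight into the verdict, or that E6011 could readily be confirmed because one arm drew more naive patients. The documents do not support that. They describe stratified central allocation and give no block size, realised stratum counts or prognostic effects. The clear reversal in the illustration needs an odds ratio more than twice the upper assumed value.

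**Conclusion.** The gap is real. Both allocation factors are absent from the deciding posterior, biologic history is in no planned model, and no adjusted result can be read against the 25-point rule. Its effect is a modest loss of precision: a shift averaging zero with a 95% range of about ±3 to 6 points (up to about 7 under the strongest odds assumed), and about 2 to 6% of verdicts changed. The chance of confirming moves by at most about 3 percentage points when the same model is compared with and without the factors. It is not a systematic bias, and it does not invalidate the planned rule.

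These sizes rest on assumed block sizes, a near-equal arm split, independent factors, an assumed placebo rate and assumed prognostic strength. The naming of sex in place of biologic history in SAP 6.8.2 rests on no assumption: it contradicts Protocol 9.1.

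**What to change.** Keep the protocol's Beta posterior as the decision rule.

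1. In SAP 6.8.1, before the remission-induction database is locked, prespecify a sensitivity analysis: a Bayesian logistic model for Week 12 CR100 with treatment, Japanese/non-Japanese and previous biologics yes/no, standardised over the FAS to a risk difference. Report P(difference ≥ 25%) beside the primary result and state any disagreement with it.
2. State the priors in advance and show the result under at least two factor-prior SDs (for example 2.5 and 5) and two treatment-prior SDs (for example 10 and 2.5).
3. In SAP 6.8.2, change male/female to previous biologics yes/no wherever the randomisation strata are defined. The supportive CR100 model in 6.8.1 then follows.

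The cost is one SAP paragraph, one model on data already collected and a short correction. No patients or assessments are added. The drawback is that at 25 patients the adjusted probability depends on the priors, so it should be read as a check on robustness and not as a second verdict.
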